2.5 Rationale for sample size

A total of 300 subjects (150 each for the MT-6548 and darbepoetin groups) should be enrolled in the treatment period. The target sample size for each cohort is shown below.

- ✓ Correction cohort: 100 subjects
- ✓ Conversion cohort: 200 subjects

However, the maximum number of subjects with mean screening period Hb values (mean of 2 most recent central testing facility results) of <11.0 g/dL and ≥ 11.0 g/dL in the screening period in the Conversion cohort should be 120.

[Rationale]

For the primary efficacy endpoint of mean Hb values at treatment period Weeks 20 and 24, the mean Hb value in the darbepoetin group is assumed to be 12.0 g/dL, the difference between the MT-6548 and darbepoetin groups is assumed to be 0 g/dL, and the standard deviation for both is assumed to be 1.78 g/dL. The non-inferiority margin is set at -0.75 g/dL. Calculation of statistical power from these assumptions shows that a sample size of 150 subjects in each group would ensure greater than 95% probability that the mean of mean Hb values in the MT-6548 group and their 95% CI would fall within the target Hb range (≥ 11.0 to < 13.0 g/dL) and non-inferiority could be established.

In addition, the target sample size was set for each of the Correction cohort, Conversion cohort, Conversion (Hb value ≥ 11.0 g/dL) cohort, and Conversion (Hb value < 11.0) cohort so that appropriate evaluation could be made for each cohort.

The assumed standard deviation was set at 1.78 g/dL based on the upper limit of the 80% confidence interval of the standard deviation in the MT-6548 300 mg group at Week 6 in study CI-0021.

3. Endpoints

3.1 Efficacy endpoints

3.1.1 Primary endpoint

Mean Hb values at Weeks 20 and 24 of the treatment period

3.1.2 Secondary endpoints

Hb values at each evaluation time point in the treatment period

- (1) Proportion of subjects with mean Hb values within the target range (≥ 11.0 to < 13.0 g/dL), < 11.0 g/dL, and ≥ 13.0 g/dL at each evaluation time point in the treatment period
- (2) Number of days from the first day of the treatment period required to reach the target Hb range (≥ 11.0 g/dL to < 13.0 g/dL)
- (3) Hb increase rate

3.1.3 Other endpoints

- (1) Changes in mean Hb values from the first day of the treatment period at Weeks 20 and 24 of the treatment period
- (2) Proportion of subjects with a ≥ 1.0 g/dL increase in mean Hb values from the first day of the treatment period at each time point of the treatment-period
- (3) Number of days to maintain the target Hb values
- (4) Proportion of subjects receiving rescue therapy with ESA formulations, red blood cell transfusion, or phlebotomy

- (5) Study drug dosage
- (6) Total number of dosage adjustments
- (7) Iron supplement dosage
- (8) Proportion of subjects receiving oral, intravenous, or (any route) administration of iron supplements
- (9) Proportion of subjects with serum ferritin ≥ 100 ng/mL or TSAT $\geq 20\%$.
- (10) Changes and rate of changes in iron-related indices (serum iron, TIBC, TSAT, and serum ferritin values) and hepcidin from the first day of the treatment period
- (11) Changes in hematocrit, red blood cell count, reticulocytes (number and rate), mean corpuscular volume, mean corpuscular hemoglobin, and erythropoietin (MT-6548 group only) from the first day of the treatment period
- (12) Changes and rate of changes in systolic blood pressure, diastolic blood pressure, lipids (total cholesterol, LDL-C, HDL-C, LDL-C/HDL-C ratio, triglycerides), and blood glucose from the first day of the treatment period
- (13) Change in renal function-related indices (eGFR, serum creatinine, urinary albumin/creatinine ratio) from the first day of the treatment period
- (14) QOL indices (EQ-5D-5L, KDQOL)

3.2 Safety endpoints

- (1) Adverse events and adverse drug reactions
- (2) Laboratory test values

- 1) Hematology tests:

Mean corpuscular volume, mean hemoglobin, mean hemoglobin concentration, RBC distribution width, WBC count, WBC fractions (neutrophils, eosinophils, monocytes, lymphocytes, basophils), platelet count

- 2) Blood biochemistry tests:

Total protein, albumin, blood glucose, urea nitrogen, creatinine, eGFR, uric acid, CPK, total bilirubin, AST, ALT, ALP, LDH, γ -GTP, Na, K, Cl, Ca, P, Mg, bicarbonate, total cholesterol, LDL-C, HDL-C, triglycerides

* eGFR is calculated according to the following formula using the age at the time of informed consent acquisition.

$$\text{eGFR (mL/min/1.73 m}^2\text{)} = 194 \times \text{serum creatinine}^{-1.094} \times \text{age}^{-0.287} (\times 0.739 \text{ if female})$$

- 3) C-reactive protein

- 4) Folic acid and vitamin B12

- 5) Vascular endothelial growth factor (VEGF)

- 6) Dehydroepiandrosterone sulfate (DHEA-S)

- 7) Urine albumin/creatinine ratio and urine protein/creatinine ratio

- 8) Urinalysis (qualitative)

- 9) Glucose, protein, urobilinogen, occult blood

- (3) Resting standard 12-lead ECG

- (4) Body weight
- (5) Vital signs
- (6) Fundoscopy
- (7) Chest X-ray
- (8) Proportion of subjects with documented Hb values of ≥ 13.0 g/dL or ≥ 14.0 g/dL
- (9) Proportion of subjects with documented Hb values of < 9.0 g/dL or < 8.0 g/dL
- (10) Proportion of subjects with a documented Hb increase rate > 0.5 g/dL/week
- (11) Hb level after dose reduction or interruption of the study drug

3.3 Pharmacokinetic endpoints

Plasma concentration of unchanged MT-6548

4. Definition of Derived Variables

4.1 Age at consent acquisition

Age (year) = Date of consent acquisition (year) – Date of birth (year)

However, when (Date of Consent [Months] < Date of Birth [Months]) or (Date of Consent [months] = Date of Birth [months] and Date of Consent [days] < Date of Birth [days]), 1 is subtracted from the traditional Japanese age system calculated above.

4.2 Duration of disease

The duration of disease (year) should be the period from the onset of renal anemia to the consent month and shall be the integer part + 1 digit (rounded). Duration of disease is calculated as follows:

Duration of disease (years) = (Date of consent acquisition [year] – Time of onset [year]) + (Date of consent acquisition [month] – Time of onset [month])/12

If the month of onset is unknown, the month is calculated as 1.

4.3 BMI

BMI (kg/m^2) = Body weight (kg)/(Height [m])²

Should be rounded and displayed to one decimal place.

4.4 LDL-C/HDL-C ratio

LDL-C/HDL-C ratio = LDL-C (mg/dL)/HDL-C (mg/dL)

Should be rounded and displayed to two decimal places.

4.5 Number of days of drug interruptions

The number of days of drug interruptions does not include subject's forgetting to take the drug and is defined by the following formula.

Number of days of drug interruptions (days) = Date of resumption of study drug administration – Start date of study drug interruption; If there are multiple interruptions, the sum of them is used.

Resumption date of study drug: After the entry of "Daily Dose" = 0 mg or 0 μ g in the CRF, the first dose should be taken when a value of >0 mg is entered for the first time, or when a value of >0 μ g is entered for the first time. If the drug interruption continues until Week 24 of the treatment period, days should be calculated based on the visit date after Week 24 of the treatment period as the resumption date. Specifically, if the treatment is completed or discontinued while the drug is interrupted, the day before the day of blood sampling at Week 24 for hematology tests or the day before the day of treatment discontinuation should be used.

Start date of study drug interruption: The dose start date when "Daily Dose" = 0 mg is first entered in the CRF or the administration date when 0 μ g is entered.

4.6 Study drug administration/duration

For subjects who completed treatment period phase I:

Study drug administration/duration (days) = Day of blood sampling for hematology tests at Week 24 – First day of the treatment period

For subjects who discontinued: Study drug administration/duration (days) = Day of discontinuation – First day of the treatment period

4.7 Study drug administration/number of administration days

The number of days that the study drug is taken (administered) is defined by the following formula.

Number of MT-6548 administration days (days) = Period of study drug administration – Number of days of no study drug administration other than drug interruptions – Number of days of drug interruptions

Number of darbepoetin alfa administration days (days) = Number of doses of darbepoetin alfa once every week \times 7 days + Number of doses of darbepoetin alfa once every 2 weeks \times 14 days + Number of doses of darbepoetin alfa once every 4 weeks \times 28 days + Number of doses of darbepoetin alfa once every 3 weeks \times 21 days + Number of doses of darbepoetin alfa twice every week \times 3.5 days

4.8 Study drug administration/compliance rate

Drug administration/compliance rate (%) = Number of days of study drug use (administration)/(Period of study drug use [administration] – Number of days of drug interruptions) \times 100

However, if the compliance rate exceeds 100%, it should be 100%.

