5.1 Efficacy analysis set

(1) FAS

The FAS consists of all randomly allocated subjects excluding the following subjects:

- ✓ Subjects who did not have anemia associated with NDD-CKD
- ✓ Subjects who have never received a dose of the study drug
- ✓ Subjects with no post-randomization efficacy data

(2) PPS

PPS is defined as the analysis set consisting of subjects excluding the following subjects from the FAS.

- ✓ Subjects who deviated from inclusion criteria
- ✓ Subjects who met any of the exclusion criteria
- ✓ Subjects who violated rules concerning prohibited concomitant drugs or therapies
- ✓ Subjects with a <80% compliance rate for either MT-6548 tablets or darbepoetin alfa injection

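### The darbepoetin compliance rate credits every dose with its full nominal interval while MT-6548 is counted in actual days, so the 80% per-protocol cut-off measures different things in the two arms and can retain control subjects with less than 80% cover

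*SAP*

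**What the plan says.** The Phase 1 SAP builds compliance in three steps.

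- **Period (4.6).** For Phase 1 completers: "Day of blood sampling for hematology tests at Week 24 – First day of the treatment period". For subjects who stop early: "Day of discontinuation – First day of the treatment period".
- **Administration days (4.7).** For MT-6548, the period less interruption days and less "Number of days of no study drug administration other than drug interruptions". For darbepoetin, a dose count: "Number of darbepoetin alfa administration days (days) = Number of doses of darbepoetin alfa once every week" times 7 days, plus the corresponding products for the other intervals (14, 28, 21 and 3.5 days).
- **Rate (4.8).** Administration days divided by the period less interruption days, times 100, in both arms. The truncation follows: "However, if the compliance rate exceeds 100%, it should be 100".

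Section 5.1 excludes from the PPS "Subjects with a <80% compliance rate for either MT-6548 tablets or darbepoetin alfa injection". Sections 8.5.1 and 8.5.4.2 use the PPS to examine the robustness of the primary non-inferiority result, which is itself an FAS analysis. Section 8.4 tabulates compliance by arm. The final SAP repeats 4.7, 4.8 and 8.4 but defines no PPS.

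**The concern.** The two numerators are different kinds of quantity. An MT-6548 subject loses a day for each day not taken. A darbepoetin subject gains a fixed block of days for each injection, whether or not those days were available before the next dose, before a recorded interruption, or before the period ended. The denominator is actual days in both arms, so only the darbepoetin ratio can carry surplus credit, and that surplus can offset a missed dose elsewhere.

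What is at stake is who is in the PPS. A robustness set should remove poorly treated subjects by the same standard in each arm. Here a control subject with well under 80% of the period covered can stay in, while an MT-6548 subject with the same uncovered days is removed. The compliance tables by arm inherit the problem.

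**Working it through.** The documents give no worked compliance figure, so there is none to reproduce. The formulas were applied directly.

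**Inputs.** P = period in days (4.6). I = interruption days (4.5, which excludes forgotten doses). n = doses given. d = nominal interval (7, 14 or 28 days in Protocol 8.3.2). Cut-off 80% (5.1). Nominal Week 24 is Day 168 (Protocol Table 9.1-1).

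**Formulas.**
- MT-6548: R = (P − missed − I)/(P − I) × 100, which cannot exceed 100%.
- Darbepoetin: R = n × d/(P − I) × 100, then truncated at 100%.
- Actual cover: sum over doses of min(d, days to next dose, days to end of period), divided by P − I.

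**Where over-credit arises (I = 0).**
1. *Early stop.* Every-4-week doses on Days 0, 28 and 84 (Day 56 missed), discontinued Day 87. Formula: 3 × 28 = 84; 84/87 = 96.6%. Cover: 28 + 28 + 3 = 59; 59/87 = 67.8%. An MT-6548 subject missing 28 of 87 days scores 67.8% and is excluded.
2. *Early dosing.* An every-2-week dose given every 12 days yields 14 doses in 168 days: 14 × 14 = 196; 196/168 = 116.7% before the cap. With four missed, on Days 48, 84, 120 and 144: 10 × 14 = 140; 140/168 = 83.3%. Cover: six gaps of 12 days and four credited at 14 days, 72 + 56 = 128; 128/168 = 76.2%.
3. *Dose on the Week 24 day.* Day 168 is an every-4-week dosing day and treatment continues into Phase 2. Neither 4.7 nor 4.8 says whether that dose counts. If it does, a completer who missed two earlier doses scores 5 × 28/168 = 83.3%, with 4 × 28/168 = 66.7% covered.

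**The cap.** min(100, R) < 80 exactly when R < 80, so truncation never changes PPS membership. It can bind only for darbepoetin, and there it hides the surplus (116.7% is shown as 100%).

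**Direction.** Largest shortfall that still scores at least 80%, on-schedule completer, P = 168:

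| | Week 24 dose not counted | Week 24 dose counted |
|---|---|---|
| MT-6548 | 33 days (135/168 = 80.4%) | not applicable |
| Weekly | 4 of 24 doses = 28 days | 5 of 25 = 35 days |
| Every 2 weeks | 2 of 12 = 28 days | 3 of 13 = 42 days |
| Every 4 weeks | 1 of 6 = 28 days | 2 of 7 = 56 days |

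In the middle column the next missed dose gives 19/24 = 79.2%, 9/12 = 75.0% or 4/6 = 66.7%. Control is therefore slightly stricter there, and looser in the right-hand column.

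The same comparison for early stops on each of Days 1 to 167, with on-schedule dosing, finds control looser on 69 stop days for every interval. It is stricter on 74 (weekly), 84 (every 2 weeks) and 89 (every 4 weeks), and equal on the rest.

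If each dose is missed independently with the same probability in both arms (completers, Week 24 dose not counted), the chance of exclusion is:

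| Miss probability | MT-6548 | Weekly | Every 2 weeks | Every 4 weeks |
|---|---|---|---|---|
| 0.15 | 4.0% | 28.7% | 26.4% | 22.4% |
| 0.25 | 93.8% | 75.3% | 60.9% | 46.6% |

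The ordering reverses between the two rows.

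**The case against.** The strongest reply is that the asymmetry runs both ways and matters little.

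- **Control is not generally favoured.** This stands. A reader might infer that the rule is looser for control and so tilts the PPS towards non-inferiority. The completer, early-stop and miss-probability results above do not support that. The documents give neither dose dates nor miss rates from which a net direction could be derived.
- **The cap is harmless to the PPS.** This stands.
- **Late doses do not hide missed doses.** This also stands. Lateness adds no credit: every-2-week dosing given every 17 days yields 10 doses and 10 × 14/168 = 83.3% with none missed, and one miss gives 9 × 14/168 = 75.0%. A late final dose can hide a delay, because its full interval is credited although the period ends first. It does not offset a miss.
- **Early stoppers carry little weight.** Largely true. The subject stopped on Day 87 has no Week 20 or 24 Hb, and the MMRM uses no imputed post-baseline values (7.4), so retention acts only through earlier visits. Completers with early dosing, or with a counted Week 24 dose, do have those values.
- **Holds are already handled.** Partly true. If the Day 56 gap had been recorded as a 0 µg hold until Day 84, those 28 days would leave the denominator and cover would be 59/59. The example assumes an unrecorded miss.

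None of this removes the basic fault: the stated rule can score a control subject above 80% when less than 80% of the period was covered.

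**Conclusion.** The definition is unsound and should be corrected, but its reach is limited. In Phase 1 it affects PPS membership and the 8.4 compliance table. In the final SAP it affects only the descriptive 8.4 table. The FAS primary analysis does not depend on it.

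Individual errors can be large: 96.6% against 67.8%, 83.3% against 76.2%, and 83.3% against 66.7% in the cases shown, each crossing the cut-off. These are illustrative patterns. The number of such subjects cannot be known from the documents, and the net effect on the PPS comparison is of unknown size and sign. The cases assume unrecorded misses, and the third also assumes that a Week 24 dose is counted.

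**What to change.** In 4.7 of both SAPs, credit each darbepoetin dose with the smallest of: its nominal interval, the days to the next dose, the days to the start of a recorded interruption, and the days to the end of the administration period. Then sum the credits. A dose on the Week 24 sampling day then earns no Phase 1 credit, which settles the open counting question. The rate can no longer exceed 100%, so the cap can go.

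This brings 4.7 into line with the use of actual dates in footnote *5 of 4.9, which already runs darbepoetin exposure from one dose to the next and stops it at discontinuation. The data exist: Protocol 9.2.2.2 has dose dates and intervals recorded in the CRF.

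Re-derive PPS membership and the 8.4 table in Phase 1, and the 8.4 table in the final analysis. If the data are already locked, report this as a labelled additional analysis with reasons, as Protocol 13.4 requires.

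The cost is one definition and a few lines of code. Darbepoetin compliance will read slightly lower, and a few control subjects may leave the PPS. The change removes over-credit only. The coarseness of interval dosing remains, so on-schedule completers still face 28 against 33 allowable missed days.

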4.9 Mean daily dose/mean weekly dose

Mean daily dose of MT-6548 during each scheduled study visit period* = (Daily dose based on the physician's prescription \times Period of administration (days)^{*3} of the corresponding dose^{*2} between the scheduled study visits*/Period between the schedule study visits (days)^{*4}

Mean weekly dose of darbepoetin alfa during each scheduled study visit period* = Daily dose based on the physician's prescription \times Period of administration (days)^{*5} of the corresponding dose^{*2} between the scheduled study visits*/Period between the scheduled study visits (days)^{*4} \times 7

*: For each period between the scheduled study visits, the actual study visit dates will not be considered, and this variable should be fixed as follows:

- ✓ The first day of the treatment period to Week 2 of the treatment period: The first day of the treatment period (Day 1) to Day 14
- ✓ Week 2 of the treatment period to Week 4 of the treatment period: Day 15 to Day 28
- ✓ The same shall apply thereafter, and the final period between the scheduled study visits should be Week 20 to Week 24 of the treatment period: Day 141 to a blood sampling day for hematological tests at Week 24 of the treatment period.

However, for subjects who discontinued their treatment, the final period between the scheduled study visits should be up to the day before discontinuation.

*2: If there are multiple applicable doses, the sum of the calculated values for each dose should be used.

*3: The number of days without drug administration other than drug interruption should not be excluded from the "period of administration (days)".

*4: 14 days up to Week 12 of the treatment period and 28 days after Week 12 of the treatment period. However, for subjects who discontinued their treatment, the final period between the scheduled study visits (days) should be the actual number of days until the day before discontinuation.

*5: "Period from the day of administration of darbepoetin alfa to the day of next administration of darbepoetin alfa". However, the first treatment period (days) during the scheduled study visit period should be "period from the start date during the scheduled study visit period to the day before the day of the first darbepoetin alfa administration date after the start date during the scheduled study visit period" and the last treatment period (days) should be "from the last day of darbepoetin alfa administration during the scheduled study visit period to the day before the day of the last treatment or the day before discontinuation during the scheduled study visit period".

The following formula should be used when no darbepoetin alfa is administered during the scheduled study visit period.

Mean weekly dose of darbepoetin alfa = Weekly dose of darbepoetin alfa immediately before the schedule study visit period

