4.9 Mean daily dose/mean weekly dose

Mean daily dose of MT-6548 during each scheduled study visit period* = Daily dose based on the physician's prescription \times Period of administration (days)^{*3} of the corresponding dose^{*2} between the scheduled study visits*/Period between the schedule study visits (days)^{*4}.

Mean weekly dose of darbepoetin alfa during each scheduled study visit period* = (Daily dose based on the physician's prescription \times Period of administration (days)^{*5} of the corresponding dose^{*2} between the scheduled study visits*/Period between the scheduled study visits (days)^{*4}) \times 7.

*: For each period between the scheduled study visits, the actual study visit dates will not be considered, and this variable should be fixed as follows:

- ✓ The first day of the treatment period to Week 2 of the treatment period: The first day of the treatment period (Day 1) to Day 14
- ✓ Week 2 of the treatment period to Week 4 of the treatment period: Day 15 to Day 28
- ✓ The same should apply thereafter, and the final period between the scheduled study visits should be Week 48 to Week 52 of the treatment period: Day 337 to the day before the day of blood sampling for hematological tests at Week 52 of the treatment period.

However, for subjects who discontinued their treatment, the final period between the scheduled study visits should be up to the day before discontinuation.

*²: If there are multiple applicable doses, the sum of the calculated values for each dose should be used.

*³: The number of days without drug administration other than drug interruption should not be excluded from the “period of administration (days)”.

*⁴: 14 days up to Week 12 of the treatment period and 28 days after Week 12 of the treatment period.

However, for subjects who discontinued their treatment, the final period between the scheduled study visits (days) should be the actual number of days until the day before discontinuation.

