4.12 Iron supplement dosage

The dose of iron supplements is defined by the following formula. However, the dose of iron supplements will not be calculated if iron supplements are used as needed.

Mean monthly dose of iron supplements during the screening period* and each scheduled study visit period** (tabulation period of iron supplements) = (Daily dose based on the physician's prescription \times Period of administration (days) of the corresponding dose*** during the tabulation period of iron supplements)/Tabulation period of iron supplements (days)**** \times 30.4375****

*: The number of days of the screening period is “First day of the treatment period – First day of the screening period”.

**: For each period between the scheduled study visits, the actual study visit dates are not considered, and this tabulation is fixed as follows:

- ✓ The first day of the treatment period to Week 2 of the treatment period: The first day of the treatment period (1 day) to 14 days
- ✓ Week 2 of the treatment period to Week 4 of the treatment period: 15 to 28 days
- ✓ The same shall apply thereafter, and the final period between the scheduled study visits should be Week 20 to Week 24 of the treatment period: 141 days to a blood sampling day for hematological tests at Week 24 of the treatment period. However, for subjects who discontinued their treatment, the final period between the scheduled study visits should be up to the day before discontinuation.

***: If there are multiple applicable doses, the sum of the calculated values for each dose should be used.

****: For subjects who discontinued their treatment, the final period between the scheduled study visits (days) should be the actual number of days until the day before discontinuation.

*****: In this tabulation, 1 month month is counted as 30.4375 days (365.25/12 = 30.4375).

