No analysis will be performed for patient cohorts.

(4) Proportion of subjects receiving rescue therapy with ESA formulations, red blood cell transfusion, or phlebotomy

The number and proportion of subjects and the 95% confidence interval (Clopper-Pearson [Exact] method) for the proportion of subjects receiving rescue therapy with an ESA preparation should be provided by treatment group, after the first day of the treatment period, in each period between scheduled study visits and during the entire treatment period from the first day to Week 24 of the treatment period.

The estimate, its 95% CI (exact method), and p-value (Fisher's exact test) for between-group difference (MT-6548 – darbepoetin) should be calculated for the proportion of subjects receiving rescue therapy.

The analyses same to the above subjects receiving rescue therapy with ESA formulation should be performed for subjects receiving rescue therapy with RBC transfusion or receiving phlebotomy.

(5) Study drug dosage

1) Study drug dosage

Descriptive statistics of the average daily dose of MT-6548 tablets and mean weekly dose of darbepoetin alfa injection should be calculated, after the first day of the treatment period, in each period between scheduled study visits and during the entire treatment period from the first day to Week 24 of the treatment period. The time course diagram for mean daily dose of MT-6548 tablets and mean weekly dose of darbepoetin alfa injection should be separately prepared by treatment group. 95% CI of the mean will be represented by an error bar. Each period between scheduled study visits is defined as the period between the scheduled visit and the day before the next scheduled visit.

2) Distribution of MT-6548 tablets and darbepoetin alfa injection

The number and proportion of subjects and the 95% CI (Clopper-Pearson [Exact] method) for the proportion per daily dose of MT-6548 tablets and per weekly dose of darbepoetin alfa during the treatment period should be provided by treatment group.

Confidential

The proportion of subjects receiving each dose of MT-6548 tablets and darbepoetin alfa injection at each evaluation time point of the treatment period should be provided as a stacked bar graph with the number of subjects in each treatment group as 100%. Stacked bar charts should be generated separately for each treatment group.

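### The MT-6548 mean dose in completers' last visit interval divides a variable number of days by a fixed 28, mis-scaling it by up to 29% (Week 20–24) or 25% (Week 48–52)

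*SAP*

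**What the plan says.** Both SAPs define the mean dose per visit interval in section 4.9. Intervals are given by day number, with the first treatment day as Day 1, and the preamble says "the actual study visit dates will not be considered, and this variable should be fixed as follows". The last interval is the exception, because it ends at an event:

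- Phase 1 SAP: "Day 141 to a blood sampling day for hematological tests at Week 24 of the treatment period".
- Final SAP: "Day 337 to the day before the day of blood sampling for hematological tests at Week 52 of the treatment period".

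Footnote *4, the same in both SAPs, sets the divisor: "14 days up to Week 12 of the treatment period and 28 days after Week 12 of the treatment period". Only subjects who discontinued have their last interval divided by actual days.

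Three other places bear on the reading:

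- Section 4.6 computes treatment duration by subtracting the first treatment day from the "Day of blood sampling for hematology tests at Week 24" (Week 52 in the final SAP).
- The study drug dosage text (Phase 1 SAP 8.5.3 (5), final SAP 8.5.2 (5)) describes each interval as "the period between the scheduled visit and the day before the next scheduled visit".
- The iron formula (Phase 1 SAP 4.12, final SAP 4.11) uses the same last interval but divides by "Tabulation period of iron supplements (days"), with no fixed 28.

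**The concern.** A time-weighted mean needs the same days in numerator and denominator. Here a completer's numerator grows or shrinks with the sampling date while the divisor stays at 28. Visit timing is then tabulated as dose variation, and the mean can exceed every dose the subject was prescribed.

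The SAPs use this last interval repeatedly: the last row of the dose-by-interval summary, the regression of dose on log CRP, the mean dose by centre, and the mean-dose endpoint of the efficacy subgroup analyses (including final SAP 8.7.3). Centre tables are exposed if centres differ in how early or late they schedule visits.

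**Working it through.** **Inputs**

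- Last interval starts on SAP Day 141 (Phase 1) or Day 337 (final): section 4.9.
- Divisor after Week 12 is 28 days: section 4.9, footnote *4.
- Week 24 window is protocol Days 161–175, nominal 168; Week 52 window is Days 357–371, nominal 364: protocol Table 9.1-1.
- The protocol calls the first treatment day Day 0 and the SAP calls it Day 1, so SAP day = protocol day + 1.
- Highest MT-6548 step is 600 mg/day: protocol 8.3.1.

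**The plan's own divisors.** Days = end − start + 1. Days 1–14 through 71–84 each give 14. Days 85–112, 113–140 and onward to 309–336 each give 28. The stated divisors are right for every interval fixed by day number.

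**The completers' last interval.** Factor = days in the interval ÷ 28.

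| | Earliest visit | On time | Latest visit |
|---|---|---|---|
| Week 24 sampling, SAP day | 162 | 169 | 176 |
| Days from 141, sampling day included | 22 | 29 | 36 |
| Factor | 0.786 | 1.036 | 1.286 |
| Day before Week 52 sampling, SAP day | 357 | 364 | 371 |
| Days from 337 | 21 | 28 | 35 |
| Factor | 0.75 | 1.00 | 1.25 |

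**In mg, at a constant dose**

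- 300 mg/day is tabulated as 235.7, 310.7 or 385.7 mg (Week 20–24) and 225, 300 or 375 mg (Week 48–52).
- 600 mg/day is tabulated as up to 600 × 36/28 = 771 mg and 600 × 35/28 = 750 mg.

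The factor does not depend on the dose pattern. With 300 mg to Day 154, then 450 mg to an early sampling day, Day 162, the formula gives (14 × 300 + 8 × 450)/28 = 278.6 mg. The true mean is 7,800/22 = 354.5 mg, and 278.6/354.5 = 0.786.

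**Less extreme timing**

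- Visits within 3 days of schedule: 26–32 days, factor 0.93–1.14 (Phase 1); 25–31 days, 0.89–1.11 (final).
- Permitted visit days with a factor above 1: 8 of 15 (Phase 1) and 7 of 15 (final).
- Each day of mismatch is worth 1/28 = 3.6%.
- The documents give no distribution of visit timing. If visits were spread evenly over the window (an assumption), the mean absolute error would be 57/15/28 = 13.6% (Phase 1) and 56/15/28 = 13.3% (final). The average factor would be 29/28 = 1.036 and 28/28 = 1.00.

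**Sensitivity to day numbering.** Applying the protocol's Day 0 numbering to Days 141 and 337 gives 0.75–1.25 and 0.71–1.21. The SAP states Day 1, so the table stands; the defect is the same either way.

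**Two values for one quantity.** In the final SAP, Week 20–24 is no longer the last interval and becomes Days 141–168 over 28, factor 1.00. Section 8.7 re-tabulates the Week 20–24 dose with the Phase 1 derivation. A subject on 300 mg/day with an on-time visit is then 300 mg under one rule and 310.7 mg under the other.

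**The case against.** The strongest reply is that the sampling day should be read as nominal: the preamble disregards actual visit dates, the dosage text speaks of scheduled visits, and the divisor is fixed. In the final SAP that reading gives Days 337–364, exactly 28 days and no error.

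It does not settle the matter. Section 4.6 uses the sampling day as an actual date, and only the last interval is defined by an event rather than a day number. In the Phase 1 SAP the nominal reading still gives Days 141–169, 29 days over 28, unless the dosage text in 8.5.3 (5) overrides section 4.9. The SAPs are translated and no program for this variable is shown, so which reading was programmed cannot be told from the documents.

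Several limits on the reach do stand:

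- Early and late visits largely cancel in a group mean. Under even spread, a constant 300 mg shifts by about 11 mg in Phase 1 and by nothing in the final analysis. What remains is inflated spread, minima and maxima, and added scatter in the CRP regression.
- Only the last row of the interval summary is affected: one of nine intervals in Phase 1, one of sixteen in the final analysis. The dose-distribution tables use prescriptions and are untouched.
- The final SAP's subgroup text (8.5.4.5) names Week 48–52, but its Table 8.5.4.5.1 names Week 20–24, where that SAP's own factor is 1.00. The effect there depends on which one is meant.
- Subgroup mean dose is summarised descriptively by arm and not tested between arms.

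**Conclusion.** The concern holds. As written, the formula multiplies the MT-6548 mean dose of a completer's last interval by 0.786–1.286 (Week 20–24, Phase 1 SAP) or 0.75–1.25 (Week 48–52, final SAP), and can return a mean above the highest dose step. These are bounds for individual subjects at the window edges; they assume an in-window visit, SAP day numbering and the sampling day taken as an actual date.

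Discontinued subjects are not affected. The factors should not be carried over to darbepoetin: it shares the 28-day divisor, but its last segment in footnote *5 runs "to the day before the day of the last treatment or the day before discontinuation during the scheduled study visit period", which does not fix a clear end day.

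The outputs concerned are descriptive or exploratory, and no Hb or non-inferiority conclusion depends on them. It should still be corrected, because the stated formula is wrong rather than merely incomplete.

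**What to change.** In section 4.9 of both SAPs, let numerator and denominator of the completers' last interval cover the same days: actual days from Day 141 (or Day 337) to the day before sampling. State this as the exception to the rule that visit dates are disregarded, and keep the existing rule for discontinued subjects. The factor is then 1.00 for any visit date.

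Fixing both parts at Days 141–168 and 337–364 would match the preamble. It needs a stated rule for visits before the nominal day, because dosing stops the day before Week 52 (protocol 8.4) and Phase 1 data are fixed at Week 24 (Phase 1 SAP section 8).

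Also align section 4.9 with the interval definition in the dosage sections, make the last segment in footnote *5 end on the same last day, and reconcile the final SAP's subgroup text with Table 8.5.4.5.1.

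The cost is edits to the interval definition and footnotes *4 and *5 in two SAPs, the consistency checks above, and a re-run of the dose summaries. No new data are needed.
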